3. DATA ANALYSIS CONSIDERATIONS

Overall analysis frame

This study is non-interventional and descriptive methods will be employed for data analyses. Descriptive analysis will be performed of all collected data, i.e. all data listed in section 2.3 ("Study variables"), except data collected only for the purpose of data cleaning. The primary and secondary outcomes of the study are presented in section 2.3.1 ("Efficacy variables").

Summary of study data

All continuous variables will be summarised using the following descriptive statistics: n (non-missing sample size), mean, standard deviation, median, 25 percentile, 75 percentile, maximum and minimum. The frequency and percentages (based on the non-missing sample size) of observed levels will be reported for all categorical measures. For variables marked "binary" exact (Clopper-Pearson) 95% confidence intervals will be calculated where appropriate. For categorical variables with more than 2 categories 95% confidence intervals will be calculated using Goodman's method or other appropriate (e.g. Sison and Glatz) method.

In general, all data will be listed, sorted by site and patient, and when appropriate by visit number within patient. All summary tables will be structured with a column for each cohort in the increasing order and will be annotated with the total population size relevant to that table/dose cohort, including any missing observations.

Baseline data

Baseline visit is a visit after physician makes a decision to prescribe Vipidia® for DM2T treatment. It means that investigator inform patient about the study only after taking decision about strategy of DM2T treatment.

Data to be collected:

- Date of visit (day, month, year)
- Date of Informed consent form signing (day, month, year)
- Compliance with Inclusion/exclusion criteria
- Demographic information: sex, date of birth, ethnicity, region of residence (city, town etc)

- Medical history and concurrent conditions: (condition, start/end date)
 - Nicotine use,
 - General medical history – body system, abnormality (ongoing or not at the study entry), date of diagnosis,
 - History of DM2T: - date of diagnosis of diabetes, historical complications of DM (diabetic retinopathy, autonomic neuropathy, diabetic nephropathy – and their date of diagnosis), family history of DM and cardiovascular diseases, previous DM2T treatment (including reason(s) for discontinuation of previous DM2T-treatment (if applicable));

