5. STATISTICAL / ANALYTICAL ISSUES

Visit windows

In accordance with the protocol, due to the non-interventional study design it's not possible to appoint exact times for the study visits, although it is expected that the period of observation will be approximately 6 months. The frequency of the visits will be assigned by each physician according to their routine practice. It is anticipated that the patients will visit their physician every 3 months and more often at the beginning.

So, for the analysis and summary of clinical laboratory, efficacy, and safety data in case of this analysis/summary performed on "by visit" base. In the event of multiple values for an assessment within an analysis window, the value closest to the scheduled visit date will be used for analyses. If two values tie as closest to the time point (for example, one value is before and the other value is after the time point), then the later value will be selected as the analysis value.

Analysis Window	Start	End	Target	Assessment to be used if duplicates
Baseline visit	<1			NA
Month 3 (Visit 2)	0	135	90	Closest to target day, if equidistant use later result.
Month 6 (Visit 3)	136	NA	180	

The definition for the study days included in each study window is defined as below:

Treatment Day prior to first dose = Visit Date – Date of First Dose

Treatment Day on or after first dose = Visit Date – Date of First Dose + 1

Adjustments for Covariates

No specific adjustments for covariates will be made in all statistical analyses, unless specified otherwise per-analysis level.

Handling of Dropouts or Missing Data

Missing efficacy outcomes will be assumed to be missing at random (MAR) and thus will not be imputed in the primary analysis. However if greater than 1% of all primary/secondary outcomes that should be available for analysis are missing, a sensitivity analysis will be undertaken in addition to the primary MAR analysis.

This sensitivity analysis will include an evaluation of the results of models developed under the assumptions of:

- 1) last observation carried forward;
- 2) worst extreme case imputation and;
- 3) regression model imputation using all available information.

Outlier identification

During data Quality Control outlier identification will be performed using adjusted Z-score method (Iglewicz and Hoaglin, 1993).

$$M_i = \frac{0.6745(x_i - \bar{x})}{MAD}$$

where MAD - Median absolute deviation, \bar{x} - median.

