8. MEASUREMENT OF EXPOSURE TO STUDY DRUG

The total duration of exposure is defined as the time interval between the first dose and the last dose, inclusive, of study drug based on the patient study drug dosing information. In case if significant (e.g. >5%) number of subjects will switch doses during the study, additional tabulation by dose will be performed (these subgroups will be defined as dosage cohorts and will be used for data tabulation / presentation purposes). Total duration (weeks) of exposure to study drug in the All Patients Enrolled population will be summarized by descriptive statistics (ie, total number, mean, standard deviation, median, minimum, and maximum) - see "Summary of study data".

Data for study subjects' compliance will be summarized and tabulated by visit.

Area under curve as product of compliance for distinct period (e.g. time between visits) and duration of this period) will be calculated and summarized.

This evaluation will be performed both for overall and for interim analysis of the study.

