9.1. Statistical Analysis of the Primary Efficacy Variable(s)

Primary study outcome - change from baseline in glycosylated hemoglobin (HbA1c) level on Vipidia® therapy (V3). Taking into account inclusion criteria (either newly diagnosed DM type 2 (drug naive) or inadequate glycemic control on previously prescribed any oral antidiabetic drug) as well as non-intervention nature of the study it is proposed to use multifactorial regression model to determine factors related to effect of Vipidia® on glycosylated hemoglobin (HbA1c) level dynamics.

Change from baseline in glycosylated hemoglobin (HbA1c) level on Vipidia® therapy (V3) in subgroups with different clinical characteristics will be summarized using relevant descriptive statistics and analyzed using Multiple Linear Regression with following predictors: prior therapy of DM, sex, age, cardiovascular risk group, therapy type (monotherapy or combined therapy), baseline BMI, initial glycemic control, T2DM duration. No subgroup analyses will be performed within interim analysis of study data.

In addition, change from baseline in glycosylated hemoglobin (HbA1c) level will be assessed and evaluated using Mixed model repeated measures (MMRM) methodology [14, 15]. The multiple visits for each patient will be incorporated as repeated measures within each patient. Visit will be treated as a categorical predictor and baseline glycosylated hemoglobin (HbA1c) level and duration of T2 DM will be included as a covariate. An appropriate covariance structure will be selected to provide estimates (Least Square Means) of change from Baseline and to perform statistical analysis at Visit 3. The dose-response trend hypothesis test will be conducted using the appropriate contrast statement for a linear (ordinal dose) trend. In addition, Least Squares Means, the associated standard errors and 95% confidence intervals will be displayed by each individual dose group.

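### The dose-response trend test in SAP section 9.1 compares physician-chosen doses with adjustment for only two patient covariates, and the SAP does not fix how dose groups are formed

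*SAP*

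**What the plan says.** Section 9.1 plans a multiple linear regression of HbA1c change on "prior therapy of DM, sex, age, cardiovascular risk group, therapy type (monotherapy or combined therapy), baseline BMI, initial glycemic control, T2DM duration". It then adds an MMRM in which visit is categorical and "baseline glycosylated hemoglobin (HbA1c) level and duration of T2 DM will be included as a covariate". From that model it wants inference at Visit 3, a linear trend test over ordered doses ("The dose-response trend hypothesis test will be conducted using the appropriate contrast statement for a linear (ordinal dose) trend"), and a display by dose: "Least Squares Means, the associated standard errors and 95% confidence intervals will be displayed by each individual dose group".

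Four other places bear on this:

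- **Section 2.1** leaves all treatment decisions to the participating physicians, so dose is not assigned by design.
- **Section 5, Adjustments for Covariates:** "No specific adjustments for covariates will be made in all statistical analyses, unless specified otherwise per-analysis level".
- **Section 8** holds the only visible definition of dose cohorts. It is conditional ("In case if significant (e.g. >5%) number of subjects will switch doses during the study, additional tabulation by dose will be performed") and states a purpose ("these subgroups will be defined as dosage cohorts and will be used for data tabulation / presentation purposes").
- **Sections 3 and 7** use cohorts without that condition. Section 3 says "All summary tables will be structured with a column for each cohort in the increasing order", and section 7 summarises medical history and medications by dosage cohort group.

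The prescribed Vipidia regimen is recorded at the baseline visit (section 3, Baseline data), but it is not named as the grouping variable for section 9.1.

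**The concern.** Because physicians choose the dose, patients on different doses may differ in ways that also predict HbA1c change. The SAP itself names such predictors in the regression. Section 2.4, citing regulatory guidance, also says the analysis of HbA1c change by baseline characteristics should account for factors correlated with the outcome. The dose comparison nevertheless carries only two of them. Its p-value would mix any dose effect with prescribing pattern, and nothing in section 9.1 labels the test exploratory.

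The grouping rule adds a second risk. If patients were classed by a dose they reached after baseline, dose changes made in response to HbA1c could create a trend where no dose effect exists. Two programmers who classed switchers differently could report different results.

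The result may be seen early. Section 5 applies the methods of sections 5 to 10 to the interim analysis of the first 350 patients, whose results are to be made public. Subgroup analyses are excluded at the interim, but the text does not say whether that covers the dose trend.

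**Working it through.** **1. The plan's own figures.** Section 2.4 gives SD 0.70, correlation 0.35, half-width 0.05 and probability 0.9. The SD of the paired difference is 0.70 × √(2 × (1 − 0.35)) = 0.798. The smallest N meeting the conditional width criterion is 1037, as stated. Dropout: 1037 / 0.75 = 1383 and 1052 / 0.75 = 1403, as stated. None of these calculations has a dose input. The sample size is therefore untouched by this point, and the trend test has no planned effect size or dose split.

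**2. Covariates side by side (section 9.1).**

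| Predictor in the regression | In the MMRM with the dose trend? |
|---|---|
| Prior therapy | No |
| Sex | No |
| Age | No |
| Cardiovascular risk group | No |
| Therapy type | No |
| Baseline BMI | No |
| Initial glycemic control | Not by that name; baseline HbA1c is in, but the SAP does not define this predictor |
| T2DM duration | Yes |

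Under the section 5 default, the six marked No stay out.

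**3. How large a non-causal difference would matter.** Inputs: N = 1052 (section 2.4), SD 0.70 and correlation 0.35 (section 2.4). Assumed: two dose groups, split 50/50 or 20/80.

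- Residual SD after baseline adjustment: 0.70 × √(1 − 0.35²) = 0.656.
- SE = 0.656 × √(1/n₁ + 1/n₂) = 0.0404 (50/50) or 0.0505 (20/80).
- Difference declared significant about half the time: 1.96 × SE = 0.079 or 0.099 HbA1c points.

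**4. Could omitted covariates reach that?** Section 2.4 plans for a partial correlation of at least 0.1. At exactly 0.1, one covariate shifts HbA1c change by about 0.1 × 0.656 = 0.066 per SD.

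- Reaching 0.079 through one covariate needs an imbalance of 0.079 / 0.066 = 1.2 SD between dose groups, which is large.
- An assumed imbalance of 0.3 SD in one covariate gives 0.3 × 0.066 = 0.020. That is 0.49 SE, for a rejection rate of about 8% at 50/50.
- As an outer case, all six omitted covariates imbalanced by 0.3 SD in the same direction give 6 × 0.020 = 0.118 before rounding. That is 2.92 SE, for a rejection rate of about 83%. Covariates that partly cancel fall in between.

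**5. Grouping rule, by simulation with no true dose effect.** 2,000 runs per setting, N = 1052, complete data, values normal with SD 0.70. Baseline correlates 0.35 with V2 and V3 (the V1–V2 value is assumed); V2–V3 correlation is 0.35 or 0.70 (assumed). Two doses, with 20%, 50% or 80% starting on the lower. Switchers move up after V2 and are those in the lower group with the highest V2/SD plus noise of SD 2. V3 change is regressed on baseline and dose group.

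| Patients switching | Rejection, grouped by last dose |
|---|---|
| 2% | 5% to 16% |
| 5% | 9% to 55% |
| 10% | 15% to 90% |

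In the same runs, grouping by baseline regimen rejects 4% to 5%. If switching is unrelated to HbA1c, last-dose grouping rejects 4% to 6%.

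The high figures depend on the switching assumptions. With noise SD 4, the ranges fall to about 6% to 19% (5% switching) and 7% to 41% (10%). If half the switches are downward and random, they are about 6% to 23% and 7% to 58%.

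**The case against.** Several points on the other side have weight.

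- **The dose term is implied.** A reader might infer that the trend test cannot be run because no dose term is named. The text does not support that. A dose contrast implies a dose factor, and the stated analysis at Visit 3 with categorical visit points to a visit-specific contrast. The gap is mostly incomplete notation.
- **Section 8 does address switching.** A reader might infer that the SAP ignores switchers. It does not, since switching is what triggers the cohorts. It is silent only on how a switcher is classed.
- **The cohort wording need not be a flat contradiction.** Section 8 makes an additional tabulation conditional. It does not say that the section 9.1 dose groups depend on the trigger, and groups by prescribed regimen can exist without switching. The mock tables also mark subgroups as included only if applicable. This softens the mismatch but does not tell the analyst which dose variable to use.
- **A more widely adjusted mixed model exists.** Section 9.2.1 plans one for HbA1c change using clinical characteristics. It names no dose term, so it does not adjust the dose comparison.
- **The study is descriptive.** Section 3 says so, and no visible objective concerns dose. That favours an exploratory label, which section 9.1 does not give. The protocol is not shown and the exploratory parts are redacted, so the point covers the visible SAP text only.

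**Conclusion.** The point stands as a cheap improvement of low severity. Followed as written, section 9.1 yields a dose-trend p-value less well adjusted than the SAP's own list of predictors allows, on a grouping it does not fix.

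That the six covariates are absent and the switcher rule unstated is clear from the text. The amount of bias is not: the SAP gives no dose split, switching rate or prescribing pattern, so size and direction are unknown. The threshold of 0.079 to 0.099 HbA1c points assumes two dose groups and only shows what the test could detect.

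Two stronger readings are not supported. One is that the trend test has a false-positive rate of 55% or 90%. Those rates need grouping by last dose, which the SAP nowhere adopts, together with the harshest of the assumed settings. The other is that the primary result is compromised. The main HbA1c change estimate does not use dose groups, and neither does the sample size.

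**What to change.** For the section 9.1 dose comparison only:

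1. Define dose groups by the Vipidia regimen recorded at the baseline visit, whether or not the section 8 switching trigger is met.
2. Write the dose and dose-by-visit terms into the MMRM and place the trend contrast at Visit 3.
3. Add prior therapy, sex, age, cardiovascular risk group, therapy type and baseline BMI. Add initial glycemic control too, unless it is defined as baseline HbA1c, which is already in the model.
4. Label the trend test exploratory and non-causal.
5. Reconcile the cohort wording in sections 3, 7 and 8 with this definition, and keep the section 8 tabulation of switching as a separate descriptive display.

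The cost is SAP wording and a few more model terms. No new data are needed, because the baseline regimen and the covariates are already planned. Baseline grouping does not describe the dose later taken, which is why the section 8 display should stay.

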9.2. Statistical Analysis of the Secondary Efficacy Variables

Secondary and exploratory outcomes will be analysed using descriptive statistics and frequencies and percentages as follows:

9.2.1. Change from baseline in glycosylated hemoglobin (HbA1c) level on Vipidia® therapy over time (V1-V2-V3) will be summarized using relevant descriptive statistics and analyzed with mixed model with repeated measures using clinical characteristics as independent factors; 9.2.2. Proportion (%) of patients with marked hyperglycemia (V2) (Marked Hyperglycemia is defined as fasting plasma glucose higher than or equal to 11 mmol/L) will be described and presented in summary tables using absolute frequencies and percentages as well as 95% confidence intervals; 9.2.3. Change from baseline in fasting plasma glucose level on Vipidia® therapy over time (V1-V2-V3) will be summarized using relevant descriptive statistics and analyzed with mixed model with repeated measures using clinical characteristics as independent factors; 9.2.4. Change from baseline in weight during Vipidia® treatment period (V1-V2-V3) will be calculated and presented in summary tables using descriptive statistics for continuous variables;

9.2.5. Change from baseline in metabolic parameters (pre- and postprandial glycemia, total cholesterol triglycerides, low density lipoproteins, high density lipoproteins) during Vipidia® treatment period (V1-V2-V3) will be summarized using relevant descriptive statistics and analyzed with mixed model with repeated measures using clinical characteristics as independent factors; 9.2.6. Proportion (%) of patients with diabetes mellitus type 2 who decrease in HbA1c $\geq 0.3\%$ over time (V1-V2-V3) will be

described and presented in summary tables using absolute frequencies and percentages as well as 95% confidence intervals;9.2.7. Healthcare resources utilization: rate of hospitalization, reasons, emergency, emergency room visits, and physician office visits; in case of hospitalization, length of stay, reason, and urgency (urgent/not urgent) will be described and presented in summary tables using absolute frequencies and percentages as well as 95% confidence intervals:9.2.8

Company Confidential Information

Company Confidential Information

Company Confidential Information

Company Confidential Information

Company Confidential Information

All of variables listed above consisting of variable changes between study visits will be additionally analyzed with appropriate statistic tests for repeated measurements (i.e. paired T-test or Wilcoxon test as appropriate).

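### Weight is the only visible continuous change-from-baseline endpoint without a mixed model, so its main V3 estimate rests on patients still observed at V3 and can be biased under the SAP's own MAR assumption

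*SAP*

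**What the plan says.** Section 2.3.1 lists change in weight over V1-V2-V3 as secondary endpoint 6, and the visit table in section 2.1 schedules vital signs at all three visits.

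Section 9.2 sets the analyses:

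- HbA1c over time (9.2.1), fasting plasma glucose (9.2.3) and metabolic parameters (9.2.5) are summarised and also "analyzed with mixed model with repeated measures using clinical characteristics as independent factors".
- Weight (9.2.4) "will be calculated and presented in summary tables using descriptive statistics for continuous variables". No model is named and no reason is given for the difference.
- The closing sentence of the section adds, for every change variable listed, a "paired T-test or Wilcoxon test as appropriate".

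On missing data, section 5 says: "Missing efficacy outcomes will be assumed to be missing at random (MAR) and thus will not be imputed in the primary analysis". It then adds that "if greater than 1% of all primary/secondary outcomes that should be available for analysis are missing, a sensitivity analysis will be undertaken". Three methods follow: last observation carried forward (LOCF), worst-case imputation and "regression model imputation using all available information".

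**The concern.** A likelihood-based mixed model uses the V2 value of a patient who leaves before V3, and under MAR this is what makes explicit imputation unnecessary. A mean or a paired test over patients with both a V1 and a V3 weight ignores that V2 value. In general it needs a stronger condition, namely that leaving is unrelated to weight change. For weight, the missing-data statement in section 5 and the method in 9.2.4 therefore do not fit together.

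If patients who gain (or lose) weight by V2 are more likely to stop, the reported V3 change describes those who stayed. Section 9, however, names all enrolled patients as the efficacy population. The sample is large, so even a modest bias can exceed the width of the confidence interval.

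**Working it through.** **The plan's own figures.** The 25% dropout and the 1052 evaluable patients come from section 2.4, where they serve the HbA1c calculations. The inflation reproduces: 1037/0.75 = 1382.7, so 1383, and 1052/0.75 = 1402.7, so 1403. The SAP states no figure for weight.

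**Inputs that must be assumed.** The SAP gives no SD of weight change, no V2-V3 correlation r, and no timing or mechanism of dropout. I take:

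- V2 change X and V3 change Y as bivariate normal, in SD units, with r = 0.5 to 0.8.
- The probability of leaving after V2 as p(x) = expit(a + ln(OR)·x), with a set so that 25% leave. OR is the odds ratio of leaving per SD of V2 change, from 1 to 3.

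**Formula.** Leaving depends on X only, so the data are MAR. The bias of the completers' mean is

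bias = r × E[X | stays], with E[X | stays] = ∫ x(1 − p(x))φ(x)dx / 0.75.

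The standard error is the completers' SD/√1052, where 1/√1052 = 0.031. The completers' SD is slightly below 1.

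**All 25% lost after V2** (absolute values):

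| OR | E[X given stays] | bias, r = 0.5 | bias, r = 0.8 | in SE |
|---|---|---|---|---|
| 1 | 0 | 0 | 0 | 0 |
| 1.5 | 0.098 | 0.049 | 0.079 | 1.6 to 2.6 |
| 2 | 0.160 | 0.080 | 0.128 | 2.6 to 4.2 |
| 3 | 0.228 | 0.114 | 0.182 | 3.8 to 6.2 |

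A simulation of 1,000,000 patients per correlation gives the same values within about 0.003 SD. In it, regressing V3 on V2 change and filling in the missing values leaves a bias of at most about 0.0025 SD at every setting, which is simulation noise. A likelihood mixed model uses the same information.

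**Half the loss before V2**, and that half unrelated to weight. Then 12.5/87.5 = 14.3% of those seen at V2 leave later. E[X | stays] falls to 0.057, 0.093 and 0.136 at OR 1.5, 2 and 3, a reduction of 40% to 42%. The largest bias becomes 0.8 × 0.136 = 0.109 SD, about 3.65 SE.

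**Coverage of a nominal 95% interval at weaker settings:**

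- OR 1.35, r = 0.7, all loss after V2: 1.7 SE, coverage 61%.
- The same with half the loss before V2: 1.0 SE, coverage 84%.
- OR 1.1, r = 0.5, all loss after V2: 0.4 SE, coverage 93%.

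**In kilograms**, if the SD of weight change were 3 to 5 kg (an assumption): 0.049 × 3 = 0.15 kg to 0.079 × 5 = 0.39 kg at OR 1.5, and at most 0.182 × 5 = 0.91 kg at OR 3.

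**The case against.** The strongest reply is that section 5 already holds a remedy. Weight is a secondary outcome, and at 25% dropout the 1% trigger is far exceeded, so regression imputation using all available data is prespecified for it. This stands, and a reader should not infer that weight is left with nothing but a completers' mean. But the imputation is only a sensitivity analysis, placed beside LOCF and worst-case imputation, neither of which is a MAR method. It is also not said to be multiple imputation, and a single imputation would understate the standard error. The main weight result remains the observed-pairs mean.

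Second, section 3 calls the study descriptive, and weight has no comparator and no role in the sample size. That lowers the stakes. It does not explain why three parallel endpoints in the same descriptive study get a model while weight, which also gets a test, does not.

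Third, parts of 9.2 and 9.3 are redacted, so a further analysis of weight cannot be ruled out. The point therefore concerns the visible text only.

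Fourth, HbA1c reduction of at least 0.3% (9.2.6) is also followed over time without a model. It is a proportion, "described and presented in summary tables using absolute frequencies and percentages as well as 95% confidence intervals", so weight stands alone only among continuous changes.

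**Conclusion.** The point holds as an inconsistency in a secondary analysis. MAR does not by itself justify the observed-pairs estimate of V3 weight change, and the plan applies a suitable method to the parallel endpoints.

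A reader might infer that the weight estimate is biased. The documents support only that it can be. MAR includes dropout unrelated to V2 weight change, where the bias is zero. Nor can a ceiling on interval coverage be stated: it ranges from the nominal 95% to almost none, depending on inputs the SAP does not give.

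Under the stated assumptions the bias is 0 to about 0.18 SD (0 to about 6 SE at 1052 completers), and roughly 40% less if half the loss precedes V2. These are large multiples of the SE partly because the sample is large; in kilograms the bias may be small.

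**What to change.** In 9.2.4, add a repeated-measures mixed model for change in weight at V2 and V3, with visit as a categorical factor and baseline weight as a covariate, plus the covariates used for the parallel endpoints if wanted. Report the LS mean change with its 95% CI at each visit as the main estimate. Keep the descriptive table and the paired tests, labelled as observed-case summaries. If weight is meant to stay descriptive, say why, and limit the MAR sentence in section 5 to likelihood-based analyses.

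The model recovers information from patients lost after V2. Those with no weight after baseline still contribute nothing to a change-from-baseline model, so their number should be reported.

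The cost is one extra run of a kind of model the SAP already uses, and a short text change. No new data are needed.
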